6.5.1.2. Demographic Characteristics

Demographic characteristics will be summarized for all subjects, as well as for the Dose 4 safety populations, and separately for the Dose 3 and Dose 4 evaluable immunogenicity populations by vaccine group and overall.

6.5.1.3. Medical History

Each reported medical history term will be mapped to a system organ class and preferred term according to MedDRA. The number and percentage of subjects with an assigned vaccine having at least one diagnosis, overall and at each system organ class and preferred term level, will be summarized by vaccine group and overall for the overall safety population.

6.5.1.4. Physical Examination

Significant physical examination findings will be recorded on Medical History or AE pages, as relevant, and reporting done under those endpoints for the overall safety population.

6.5.1.5. Blood Samples for Assay

The number and percentage of randomized subjects providing blood samples within and outside of protocol pre-specified time frames will be tabulated separately for Dose 1 to Dose 3 and Dose 4.

CCL

6.5.2. Study Treatment Exposure

6.5.2.1. Vaccination Timing and Administration

The number and percentage of subjects randomized and receiving each vaccine (20vPnC or 13vPnC) within the protocol-specified time frame, as well as before and after the specified time frame, will be tabulated for each vaccine group and overall for all randomized subjects. The denominator for the percentages is the total number of subjects in the given vaccine group or overall. In addition, the relation of randomized vaccine to actual vaccine received will be presented as a cross tabulation of the actual vaccine received versus the randomized vaccine

[figure not shown]
6.5.3. Prior/Concomitant Vaccination and Concomitant Medications Used to Treat SAEs and NDCMCs

Each prior/concomitant vaccine will be summarized according to the Anatomic Therapeutic Chemical (ATC) 4th level classification. The number and percentage of randomized subjects receiving each vaccine (including DTaP-IPV-HebB (Pediarix, supplied to study sites, containing diphtheria, tetanus, acellular pertussis, inactivated poliovirus, and hepatitis B antigens), rotavirus, Hib, MMR, varicella, influenza, others) will be cross tabulated according to assigned vaccine regimen. Summarization will be done separately for before Dose 1, between Dose 1 and 1 month after Dose 3, between 1 month after Dose 3 and Dose 4, and between Dose 4 and 1 month after Dose 4. The Dose 1 to Dose 3 safety population will be used for the last one.

Concomitant medications used to treat SAEs and NDCMCs will be summarized for the time points Dose 1 to 6 months after Dose 4 (safety population), and for the separate time points Dose 1 through 1 month after Dose 3 (Dose 1 to Dose 3 safety population), from 1 month after Dose 3 to Dose 4 (Dose 1 to Dose 3 safety population), Dose 4 to 1 month after Dose 4 (Dose 4 safety population), and from 1 month after Dose 4 to 6 months after Dose 4 (After Dose 4 safety population).

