4.1. Safety Analysis Population

The **overall safety population** will include all subjects who receive at least 1 dose of study vaccine (20vPnC or 13vPnC) and have safety data reported in the study. Subjects will be assigned to vaccine group corresponding to the vaccine actually received. The safety population will be the analysis population for safety and reactogenicity endpoints.

Separate safety populations will be defined for each vaccination as follows:

Dose 1 to Dose 3 Safety Population - Subjects receiving Dose 1 and having safety data between Dose 1 and the blood draw visit 1 month after Dose 3

Dose 4 Safety Population - Subjects receiving Dose 4 and having safety data between Dose 4 and 6 months after Dose 4

If a subject's actual vaccine dose varies within a particular safety population (eg, overall or Dose 1 to Dose 3), the subject data will be either analyzed for any by-dose presentation, or data will be presented in listings as appropriate.

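### SAP 6.5.3 gives the wrong population for the concomitant-vaccine summary after Dose 4: it names a set that does not require Dose 4

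*SAP*

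**What the plan says.** The vaccine paragraph of SAP 6.5.3 describes its table as "The number and percentage of randomized subjects receiving each vaccine", which "will be cross tabulated according to assigned vaccine regimen". It sets four intervals: before Dose 1, Dose 1 to 1 month after Dose 3, and then "between 1 month after Dose 3 and Dose 4, and between Dose 4 and 1 month after Dose 4". The next sentence assigns a population to one of them: "The Dose 1 to Dose 3 safety population will be used for the last one". Read in order, that is the interval starting at Dose 4. No population is named for the other three.

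SAP 4.1 defines the two populations that matter here:

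- "Dose 1 to Dose 3 Safety Population - Subjects receiving Dose 1 and having safety data" up to the blood draw visit 1 month after Dose 3.
- "Dose 4 Safety Population - Subjects receiving Dose 4 and having safety data" from Dose 4 to 6 months after it.

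The following paragraph of SAP 6.5.3, on concomitant medications, covers the same interval and assigns it differently: "Dose 4 to 1 month after Dose 4 (Dose 4 safety population".

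**The concern.** The first of these populations has no Dose 4 requirement. An infant who received Dose 1, had some safety data and withdrew before Dose 4 belongs to it, yet has no interval after Dose 4 in which a concomitant vaccine could be counted. That infant can only add to the denominator. SAP 6.5.1.1 plans to count withdrawals between 1 month after Dose 3 and Dose 4, so the SAP itself allows for such infants.

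The table shows how many infants in each group received optional vaccines around Dose 4. MMR is one: Protocol 5.10.2 permits it at the same visit. This is context for reading the Dose 4 reactogenicity results, and the figure wanted is uptake among infants who received Dose 4. The rule as written does not give it. A programmer also meets a general reference to randomized subjects at the start of the paragraph, a narrower set at its end, and a third set for the same interval in the next paragraph.

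**Working it through.** No figure in the documents depends on this sentence, so there is no stated number to reproduce. The check is a comparison of text, followed by arithmetic for the size.

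**1. Populations assigned to Dose 4 data in the SAP**

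| Place | Data | Population for Dose 4 data |
|---|---|---|
| 6.1.1.1 | Local reactions | Dose 4 safety |
| 6.1.2.1 | Systemic events | Dose 4 safety |
| 6.1.3.1 | AEs, two intervals | Two populations listed, in the same order as the intervals; Dose 4 safety is second |
| 6.5.3, medications | Dose 4 to 1 month after | Dose 4 safety |
| 6.5.3, vaccines | Dose 4 to 1 month after | Dose 1 to Dose 3 safety |

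The last row stands alone. The sentence is complete, 6.5.3 carries no redaction mark, and SAP 1 records this as version 1, so neither redaction nor superseded text explains it.

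The medication paragraph has a fault of its own. Its final interval reads "from 1 month after Dose 4 to 6 months after Dose 4 (After Dose 4 safety population", a label SAP 4.1 does not define. The conclusion does not rest on that paragraph alone, because 6.1.1.1 and 6.1.2.1 support it independently.

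**2. Effect on the printed percentage**

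Let u be uptake of a given vaccine among Dose 4 recipients, and m the share of the Dose 1 to Dose 3 safety population who did not receive Dose 4. Then:

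- Printed percentage = u × (1 − m)
- Shift = u × m

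The documents give neither u nor m, so both are assumptions here. The upper value of m borrows the 15% dropout in Protocol 3.3. That is a planning figure for immunogenicity evaluability, not a rate of missing Dose 4.

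| u | m = 0 | m = 5% | m = 10% | m = 15% |
|---|---|---|---|---|
| 60% | 60.0% | 57.0% | 54.0% | 51.0% |
| 80% | 80.0% | 76.0% | 72.0% | 68.0% |
| 95% | 95.0% | 90.25% | 85.5% | 80.75% |

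The largest shift in this grid is 0.95 × 0.15 = 14.25 percentage points. The shift is zero if every infant receives Dose 4.

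**3. An example in counts**

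Take 230 infants in one arm (Protocol 3.3) and assume all are in the Dose 1 to Dose 3 safety population. Assume 200 receive Dose 4, so m = 30/230 = 13.0%, and that 160 of those receive the vaccine.

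- Rule as written: 160/230 = 69.6%.
- Dose 4 safety population, if all 200 have safety data after Dose 4: 160/200 = 80.0%.

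**4. Can a reader recover the right figure?**

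Largely, yes. The numerator does not change, because infants without Dose 4 cannot be counted in it. SAP 6.5.1.1 reports the number who received Dose 4 by randomized group, and 6.5.3 tabulates by assigned regimen, so the groups match. In the example the printed count of 160 over the 200 in the disposition table returns 80.0%. What remains is any Dose 4 recipient with no safety data afterwards, who would be in the disposition count but outside the Dose 4 safety population.

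**The case against.** The strongest counter-argument is that the population may be right and the pointer wrong. The medication paragraph pairs the Dose 1 to Dose 3 safety population with the interval from 1 month after Dose 3 to Dose 4. If the vaccine sentence was meant for that third interval, its population fits. The documents do not settle which slip occurred. But under this reading the Dose 4 interval has no population at all and still needs one, so the sentence must be corrected either way.

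It can also be said that a common denominator carried across intervals is not an error in itself. SAP 6.5.1.5 and 6.5.2.1 report against randomized subjects, Dose 4 procedures included, and a sentence specific to one interval would normally override a general opening phrase. That is fair for an openly stated all-randomized denominator. The set named here is neither all randomized subjects nor Dose 4 recipients, so this does not justify it.

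Two objections stand in part. The size is illustrative: only the direction is certain, namely that the printed percentage is at or below uptake among Dose 4 recipients. And SAP 4.1 groups safety populations by vaccine actually received while 6.5.3 tabulates by assigned regimen. That mismatch exists under either population; correcting the population neither creates nor removes it.

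**Conclusion.** The concern holds, as a minor one. SAP 6.5.3 assigns an interval that begins at Dose 4 to a population that does not require Dose 4, against its own next paragraph and the rest of the SAP. Read literally, it understates uptake among Dose 4 recipients by the factor 1 − m.

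Under the assumed ranges (uptake 60% to 95%, 0% to 15% without Dose 4) the understatement runs from 0 to about 14 points. The upper end needs both the highest assumed uptake and the borrowed 15%. One descriptive table is affected. No primary or secondary endpoint estimate changes, and SAP 5.1 states that there are no hypothesis tests or formal decision rules. Confidence is high that the conflict exists; which of the two slips produced it cannot be told from the documents.

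**What to change.** Replace the last sentence of the vaccine paragraph in SAP 6.5.3 with:

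> The Dose 4 safety population will be used for the last one; for that interval, percentages are based on subjects in that population rather than on all randomized subjects.

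Keep the tabulation by assigned regimen as it stands. The cost is one sentence in the SAP, with no new data and no protocol change.

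Two neighbouring items are separate from this correction but could be tidied in the same edit: naming the population for the first three vaccine intervals, and defining or correcting the population label on the last medication interval.

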6.6. Safety Summaries and Analyses

The safety measures local reactions, systemic events, AEs, SAEs and NDCMCs summaries and analyses are described under the Primary Endpoints (see Section 6.1).

9. APPENDICES

Appendix 1. DATA DERIVATION DETAILS

Appendix 1.1. Definition of Protocol Deviations that Relate to Statistical Analyses/Populations

Appendix 1.1.1. Deviations Assessed Prior to Randomization

Any significant deviation from the protocol, including inclusion and exclusion criteria, will be reviewed prior to database lock and a decision made regarding evaluation for each analysis population.

Appendix 1.1.1. Deviations Assessed After Randomization

Any significant deviation from the protocol, including inclusion and exclusion criteria, will be reviewed prior to database lock and a decision made regarding evaluation for each analysis population.
